5.0 Sample Size

A total size of 22 subjects is estimated, who will provide both eyes for the analysis.

5.1 Sample Size Calculation

Although there are no references on sample calculation in phase I studies, it was considered pertinent to do so according to the presence of Adverse Events (AE) reported by Macejko et al., 2010 [1], in a multicenter, double-blind, randomized, parallel-group controlled clinical trial. Where the efficacy and tolerability of a 1.5% bepotastine besilate ophthalmic solution (n=43) versus 1.0% bepotastine (n=44) and placebo (n=43) were evaluated in 130 subjects in a conjunctival allergen challenge (CARC) model.

The intervention consisted of the application of 3 drops in each eye of each of the interventions (3 minutes after the RAC), with measurements at 15 minutes, 8 and 16 hours post-instillation.

The percentage of adverse events was 30% for the 1.5% bepostatin group, 47.5% for 1% bepostatin, and 22.5% for placebo, so a non-inferiority margin of 10% was considered with the formulation proposed in this protocol (1.5% bepostatin) [1].

The sample size was calculated using the equation for a proportion [2], considering a power of 80% (β), a significance level of 0.05 (α) and a non-inferiority margin (δ) of 10%.

Hypothesis

$$H_0: p - p_0 \leq \delta$$

$$H_1: p - p_0 > \delta$$

Where, δ is the non-inferiority margin (-10%).

Equation

The calculation to estimate the sample size and power was performed using the following equations.

$$n = p(1-p) \left(\frac{z_{1-\alpha} + z_{1-\beta}}{p - p_0 - \delta} \right)^2$$

$$1 - \beta = \theta(z - z_{1-\alpha}) + \theta(-z - z_{1-\alpha}), z = \frac{p - p_0 - \delta}{\sqrt{\frac{p(1-p)}{n}}}$$

Where:

n is the sample size,

p_0 is the reference proportion,

θ is the normal distribution function,

α is the Type I error

β is the Type II error, which means that, $1 - \beta$ is the power, and

δ is the test margin.

Calculated sample: According to the previous calculation, the result is 18 subjects; this calculation was increased by 20% to account for possible losses. The total required sample size is 22 subjects, who will provide an input for the analysis.

6.0 Statistical Analysis Plan [3]

6.1 Primary outcome variables:

- Incidence of unexpected AEs related to the investigational product.
- ICO score.

6.2 Secondary outcome variables:

- Changes in Corrected Visual Acuity (CCVA).
- Corneal and conjunctival staining changes with lissamine green.
- Corneal and conjunctival staining changes with fluorescein.
- Changes in conjunctival hyperemia.
- Incidence of chemosis.

Table 3. Operational Definition of the Variables

| Variable | Conceptual Definition | Operational Definition | Type of measurement | Normal value | Statistical test |
|-----------------------------------|--|--|--|---|---|
| Adverse events | Any adverse medical event that occurs in a patient or clinical research subject who has been administered a pharmaceutical product and that does not necessarily have a causal relationship with this treatment. [4] | Adverse events occurring during the study will be collected using the electronic CRF. | 
 • Continuous quantitative. • Qualitative categorical. | 
 • Frequency: Subjects presenting AE/Total number of exposed subjects. • Intensity: 0= Mild 1= Moderate 2= Severe • Causality: 0=Probably or possibly related. 1=Unlikely related. | 
 • χ^2 or Fisher's Exacta. |
| Ocular Comfort Index (OCI) score. | The OIQ is a questionnaire designed to measure ocular surface irritation. It assesses symptoms focused on comfort associated with ocular surface disorders. Higher values indicate more severe symptoms. | The evaluator will administer the questionnaire to the subject and allow him or her to answer it calmly without any pressure or coercion. See Appendix 10.1, ICO . | Discrete quantitative. | 
 Score: 0=None, 100=High discomfort. | 
 • Wilcoxon rank test. |
| Changes in visual ability. | Best-corrected visual acuity (BCVA) is a test of visual function. Spatial VA is the ability to distinguish separate | Snellen chart | Discrete quantitative. | 
 Fraction, normal value = 0.6 to 2.0 | 
 • Wilcoxon rank test. |

| | | | | | |
|--|---|--|---|--|---|
| 
elements of an object and identify them as a whole. It is quantified as the minimum angle of separation (located at the nodal point of the eye) between two objects that allows them to be perceived as separate objects.
 | Degrees: | 
The staining is presented in a series of panels (AE). The staining points range from 0-5 for each panel and from 0-15 for the total exposed area of conjunctiva and cornea.
 | 
 • χ^2 or Fisher's Exacta. | | |
| 
Corneal and conjunctival staining changes with lissamine green.
 | 
Detection of epithelial defects in the conjunctiva and cornea.
 | 
Direct observation with a slit lamp, Oxford scale graduation. See Appendix 10.3, Oxford Scale .
 | 
Qualitative Ordinal
 | 
The staining is presented in a series of panels (AE). The staining points range from 0-5 for each panel and from 0-15 for the total exposed area of conjunctiva and cornea.
 | 
 • χ^2 or Fisher's Exacta. |

| | | | | | |
|---------------------------------|--|---|--------------------------|--|--------------------------------|
| Conjunctival hyperemia changes. | It is defined as the simplest reaction of the conjunctiva to a stimulus; a red appearance is observed secondary to vasodilation of the vessels of the conjunctiva of variable intensity. | Direct observation. Classification using the Efron scale. See Appendix 10.2, Efron Scale for Conjunctival Hyperemia . | Ordinal qualitative. | Degrees: 0=Normal, 1= Very mild, 2= Mild, 3= Moderate, 4= Severe. | • χ^2 or Fisher's Exacta. |
| Incidence of Chemosis. | It is defined as conjunctival edema resulting from an inflammatory reaction. It is classified as present or absent. | The evaluator will use a narrow beam of light at 60° and measure whether the conjunctiva separates from the sclera by $\geq 1/3$ of the total eyelid opening or if it extends beyond the gray line. | Qualitative categorical. | 0=Absent 1= Present | • χ^2 or Fisher's Exacta. |

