**Figure 3. Adverse event care**

During the development and conduction of this study, events may occur in the subject under investigation.

harmful undesirable or adverse reactions, of medical implication, which do not necessarily have a causal relationship with the PI or investigational drug. These harmful phenomena may occur during the use of investigational medicinal products at doses authorized for use in humans, by a local, national or international regulatory body. However, there may be a suspicion that the IP or the investigational drug may cause any undesirable clinical manifestation. The AEs, ADRs or SRAs to one or several medications may occur during the systematic evaluation of participants (on days in that the clinical review is scheduled, according to the schedule of activities) or suddenly, in such a way that:

1. The researcher must be the first person to whom the patient notifies that he or she has developed or presented with any harmful clinical phenomenon during his or her participation in the present study.
2. Based on clinical judgment, the principal investigator will determine the appropriate course of treatment for the adverse event/reaction based on the relevant physical examination, history, etc., as well as the analysis of information available in the medical literature and the information contained in the investigator's manual, Prescribing Information, or the comparator drug's data sheet.
3. Such care may be provided at the research center or at the hospital with the highest capacity for treatment. Thus, if the patient is referred by the PI to a hospital, they will receive care through a referral system. The referral may be through a card identifying the subject as a study participant and linking them to the pre-established agreement with the institution, or through a referral medical note issued by the PI. Laboratorios Sophia, SA de CV, will pay the costs for medical care for participating patients when the adverse event is associated with or related to the PI or investigational drug.
4. Taking into account the clinical information collected, either during the care provided at the research center or provided by the treating physician(s) at the hospital, the IP will record the AE in his/her clinical note, noting the seriousness, intensity (mild, moderate, or severe), and relationship with the product or drug under investigation.

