### 10.1.5 Subjects included in the analysis

Those subjects who meet an adherence  $\geq 75\%$  will be included in the statistical analysis for meet the objective of the study, taken from the weight of the PI.

The investigational drug will be considered safe and tolerable when present in less than 10% of the study population unexpected adverse events related to the investigational product.

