3.0 Study Hypothesis

H_0 : PRO-172 ophthalmic solution is safe and tolerable in its ophthalmic application, presenting in less than 10% of the study population unexpected adverse events related to the investigational product.

H_1 : PRO-172 ophthalmic solution is not safe and tolerable for ophthalmic application, as it presented unexpected adverse events related to the investigational product in less than 10% of the study population.

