For adverse event reporting, all eyes of participants assigned to the intervention after the baseline visit will be considered. Results will be expressed as a percentage of subjects.

The final results report will be displayed in tables or graphs, as appropriate.

Table 3. Triangulation of concepts [5]

| Variable type | Variable | A1 | B1 | B2 | C1 | C2 | D1 | D2 | D3 | D4 |
|--------------------------|---|----|----|----|----|----|----|----|----|----|
| Background | | | | | | | | | | |
| A1 | Demographics | | | DT | | | | | | |
| Basal | | | | | | | | | | |
| B1 | Medical record | | | DT | | | | | | |
| B2 | Comprehensive ophthalmological evaluation | | DT | | TB | | | | B | |
| Security | | | | | | | | | | |
| C1 | EAs | | | | TB | B | B | TB | TB | TB |
| C2 | ICO | | DB | | B | B | | | | |
| Secondary outcome | | | | | | | | | | |
| D1 | MAVC | | DB | | B | | B | | | |
| D2 | Ocular surface stains (TF and TVL). | DT | | | T | | | T | | |
| D3 | Conjunctival hyperemia | TD | | DT | T | | | | T | |
| D4 | Chemosis | TD | | DT | T | | | | | T |

D. Descriptive statistics; T, 2x2 contingency table; B, Bivariate analysis; M, Multivariate analysis.

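### The SAP's operational row for the primary adverse-event variable defines an any-AE frequency, which does not match the unexpected-and-related rate judged against 10%, and expectedness is not a listed AE item.

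*SAP*

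**What the plan says.** SAP 6.1 lists the first primary outcome as "Incidence of unexpected AEs related to the investigational product". SAP 3.0 sets the limit on the same event: the product is safe if "presenting in less than 10% of the study population unexpected adverse events related to the investigational product". Protocol 10.1.5 repeats this as the decision rule: the drug "will be considered safe and tolerable when present in less than 10% of the study population unexpected adverse events related to the investigational product".

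The outcome becomes a number in the SAP's Table 3, Operational Definition of the Variables (section 6.0). Its adverse-event row takes the general definition of an AE, one "that does not necessarily have a causal relationship with this treatment", and gives the measure as "Frequency: Subjects presenting AE/Total number of exposed subjects". The row carries an intensity code and a causality code, "0=Probably or possibly related. 1=Unlikely related". It has no code for expected or unexpected.

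SAP 7.0 adds no filter: "For adverse event reporting, all eyes of participants assigned to the intervention after the baseline visit will be considered", with results given as a percentage of subjects. The triangulation table in the same section lists only AEs in general. Protocol Table 3 (section 7.3.3) likewise lists AEs as a count and as present or absent.

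On data capture, protocol 8.4.1 lists what the AE record takes into account, including dates, diagnosis, outcome, batch, dechallenge and rechallenge. Protocol 8.4.3, step 4, has the investigator write the clinical note "noting the seriousness, intensity (mild, moderate, or severe), and relationship with the product or drug under investigation". Neither list includes expectedness.

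The protocol does say which AEs are expected. Section 7.3.3.1 names eight: dysgeusia, eye irritation, headache, nasopharyngitis, dry eye, ocular itching, nasal congestion and rhinorrhea. Section 2.4.1 names dysgeusia and one transient effect (heartburn in the translated text) and anticipates no other risks.

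**The concern.** A primary endpoint defined by two attributes, relatedness and unexpectedness, needs a rule that applies both. The SAP's rule applies neither. It codes one of them, causality, and has no code for the other. A programmer working from the table alone would produce a rate that is not the one in the hypothesis.

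An analyst who notices the mismatch has to supply the missing classification. The SAP does not say which list governs, who applies it, or when. Headache, for example, is expected under protocol 7.3.3.1 and absent from 2.4.1. The trial is open-label and the analysis is done by sponsor staff (protocol 10.1.1, SAP 7.0), so nothing in the plan prevents the deciding attribute from being assigned once the events are known. With about 22 subjects, reclassifying one subject can change the conclusion.

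**Working it through.** **1. The plan's own figure.** Protocol 10.2.2 and SAP 5.1 give 18 subjects, raised by 20% to 22. The documents do not say which planning rate is p and which is p0. One reading reproduces the figure: one-sided alpha 0.05, power 80%, p = 0.30, p0 = 0.475, margin 0.10.

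n = p(1−p) × [(z(1−α) + z(1−β)) / (p − p0 − δ)]² = 0.21 × [(1.645 + 0.842) / (−0.275)]² = 17.17, rounded up to 18. Then 18 × 1.2 = 21.6, rounded up to 22.

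Other inputs also land near 18, so this is a plausible route and not a confirmed one. The planning rates (30%, 47.5%, 22.5%) are described only as percentages of adverse events, so the sample size does not rest on the unexpected-related rate either.

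**2. The two numerators side by side.**

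| Item | Outcome judged against 10% (SAP 3.0, 6.1; protocol 10.1.5) | Operational row (SAP 6.0) |
|---|---|---|
| Event counted | AE that is unexpected and related | Any AE |
| Relatedness | Required | Coded, not applied to the frequency |
| Expectedness | Required | No code |
| Denominator | Study population | Exposed subjects |

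**3. What below 10% means in subjects.** 2/22 = 9.1% passes and 3/22 = 13.6% fails, so at most 2 subjects may have the event. This cut-off needs more than 20 subjects in the analysis: 2/20 = 10.0% already fails.

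**4. Probability of failing, N = 22.** P(fail) = 1 − Σ(k=0 to 2) C(22,k) p^k (1−p)^(22−k).

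At p = 0.30 the three terms are 0.0004, 0.0037 and 0.0166. They sum to 0.0207, so P(fail) = 0.979, with 22 × 0.30 = 6.6 subjects expected.

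| Numerator | Rate | Source | P(fail) |
|---|---|---|---|
| Any AE | 30% | Planning rate, 1.5% arm | 97.9% |
| Any AE | 22.5% | Planning rate, placebo arm | 90.1% |
| Unexpected and related | 1% | Assumed | 0.1% |
| Unexpected and related | 2% | Assumed | 0.9% |
| Unexpected and related | 5% | Assumed | 9.5% |
| Unexpected and related | 10% | Assumed | 38.0% |
| Unexpected and related | 15% | Assumed | 66.2% |

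The documents give no rate for unexpected related AEs, so the last five rows are a range and not an estimate.

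**5. Sensitivity to the number analysed.** With 18 subjects the rule allows 1 (1/18 = 5.6%). P(fail) is then 98.6% at 30%, 5.0% at 2% and 22.7% at 5%. The contrast between numerators remains.

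**The case against.** The strongest reply is that the plan names the right endpoint and the table row merely describes the collected variable. This is largely correct. SAP 6.1 stands just above the table, and SAP 3.0, protocol 3.4.1 and protocol 10.1.5 all tie the 10% to unexpected, related events. A reader might infer that the SAP compares an any-AE rate with 10% and so nearly guarantees a verdict of not safe. The documents do not support that: no section applies 10% to any AE, and an analyst would have to set aside the named outcome, the hypothesis and the decision rule to get there.

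A reader might also infer that expectedness is never recorded. That goes too far. The case report form itself is not in the documents, and protocol 8.4.1 describes what the record considers without being a field specification. The diagnosis is recorded, so an event term could be checked against the pre-specified list in protocol 7.3.3.1. Protocol 8.5 also has the investigator report unanticipated problems that are unexpected and related. That route covers only a subset, because it also requires an indication of increased risk.

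Nor does any section hand the classification of expectedness to the sponsor. Late classification by sponsor staff is a possibility the plan leaves open, not something it prescribes.

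What survives is the mismatch. The one stated calculation rule yields a different quantity from the endpoint, the SAP cites no expected-AE list, and the protocol's two lists differ. Protocol 8.4.3 adds a third source by pointing to the investigator's manual for expected events.

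**Conclusion.** The concern holds as a wrong stated rule for the primary variable together with a missing reference for expectedness. The endpoint itself has not been changed: it is named correctly and consistently, and its derivation is what fails.

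The contrast between 97.9% and 0.9% to 9.5% illustrates how far apart the two numerators can be. It does not predict this trial's result. It assumes that all 22 subjects are analysed and that the 30% rate from an allergen-challenge study carries over to healthy subjects, which is uncertain. The 2% and 5% rates are assumptions. The mismatch in definition depends on none of these figures.

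**What to change.** 1. In the SAP's operational-definition table, replace the frequency line for the primary variable with: number of subjects with at least one AE coded both related and unexpected, divided by the number of exposed subjects.
2. Name the list in protocol 7.3.3.1, reconciled with 2.4.1, as the single reference for expectedness, and cite it in the SAP.
3. Have the investigator record expected or unexpected when each AE is entered, and lock that field before analysis.
4. State which causality categories count as related. Protocol 8.3 has six, and the SAP's two codes leave no place for certain, conditional or not classifiable.
5. Keep any-AE frequency as a separate descriptive row.

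The cost is a revised SAP row plus one descriptive row, one case-report-form field and a short protocol clarification. The sample size does not change.

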7.0 Methods of Analysis [5]

Statistical analysis will be performed by personnel from Laboratorios Sophia, SA de CV. SPSS version 19.0 (IBM Corporation, Armonk, NY, USA) will be used. Coding will be performed using consecutive numbers. Data will be collected and organized in an Excel spreadsheet (Microsoft® Office). The data will then be exported to the SPSS platform. Variables will be categorized according to their nature (see [Table 2](#)).

Study participants will be identified by a number and their initials.

The initials of the subject of study will be obtained starting with the first letter of the name, followed by the first letter of the first surname and the first letter of the second surname, obtaining a maximum of three letters. In case the person has two names or a compound surname, the first letter will always be used.

Example:

A. [name]

B. [name]

a. Initials: AMC

b. Initials: JDO

Once the subject has been selected, they will be assigned a number that will identify them throughout the study. This code will consist of eight numbers in the following order from left to right:

- three digits of the molecule under study according to the name given by the sponsor.
- two digits corresponding to the research center number.
- three digits of the consecutive number assigned to its inclusion in the research center.

The Kolmogorov-Smirnov test will be performed to determine the distribution of the results obtained. [3]

The results of continuous quantitative variables will be presented in measures of central tendency: mean, standard deviation and ranges.

The statistical analysis of continuous quantitative variables to find significant differences (p) will be as follows:

- Intra-group analysis: They will be determined using the Wilcoxon rank test for quantitative variables. [6]

The level of difference to consider significance will be an alpha (α) of 0.05 or less.

The results of the nominal and ordinal qualitative variables will be presented in frequencies, proportions and percentages.

Statistical analysis to identify significant differences in qualitative variables will be performed by creating 2x2 contingency tables and will be carried out as follows:

- Intra-group analysis: Pearson's Chi-square (χ^2) test or Fisher's exact test for expected values less than 5.

The level of difference to consider significance will be an alpha (α) of 0.05 or less.

For adverse event reporting, all eyes of participants assigned to the intervention after the baseline visit will be considered. Results will be expressed as a percentage of subjects.

The final results report will be displayed in tables or graphs, as appropriate.

Table 3. Triangulation of concepts [5]

| Variable type | Variable | A1 | B1 | B2 | C1 | C2 | D1 | D2 | D3 | D4 |
|--------------------------|---|----|----|----|----|----|----|----|----|----|
| Background | | | | | | | | | | |
| A1 | Demographics | | | DT | | | | | | |
| Basal | | | | | | | | | | |
| B1 | Medical record | | | DT | | | | | | |
| B2 | Comprehensive ophthalmological evaluation | | DT | | TB | | | | B | |
| Security | | | | | | | | | | |
| C1 | EAs | | | | TB | B | B | TB | TB | TB |
| C2 | ICO | | DB | | B | B | | | | |
| Secondary outcome | | | | | | | | | | |
| D1 | MAVC | | DB | | B | | B | | | |
| D2 | Ocular surface stains (TF and TVL). | DT | | | T | | | T | | |
| D3 | Conjunctival hyperemia | TD | | DT | T | | | | T | |
| D4 | Chemosis | TD | | DT | T | | | | | T |

D. Descriptive statistics; T, 2x2 contingency table; B, Bivariate analysis; M, Multivariate analysis.

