### **7.3.3.3 Visual Acuity with correction**

Visual acuity (VA) is a test of visual function. Spatial VA is the ability to distinguish separate elements of an object and identify them as a whole. It is quantified as the minimum angle of separation (located at the nodal point of the eye) between two objects that allows them to be perceived as objects separated.

Snellen notation is described as the distance at which the test is performed, divided by the distance to the which the letter is equivalent vertically to 5 minutes of arc. Thus, at 6 meters a letter 6/6 (20/20) is equivalent to 5 minutes of arc, a letter 6/12 (20/40) is equivalent to 10 minutes, and a letter 6/60 (20/200) is equivalent to 50 minutes. The Snellen fraction can also be expressed as a decimal (i.e. 20/20 = 1 and 20/40 = 0.5).  
[44]

VA will be assessed at baseline, without refractive correction, using the Snellen chart. It will be placed in a place with adequate lighting, natural or artificial and at a distance of 3m from the subject to be evaluated. The visual acuity of each eye will be taken, starting with the right eye (RE) asking the subject to maintain both eyes open and using an occluder to cover the left eye (OS); the subject will read aloud the lines that the evaluator points out, the line of smallest letters that the evaluator can see will be noted by the evaluator as a fraction as the AV of OD in the clinical record. The OS is carried out using the same method.

Subsequently, the objective and subjective refractive correction of the subject will be performed. The result of the Subjective refraction will be reported as AVcc, and will be noted as a fraction in the clinical record and on the eCRF, In addition, the eCRF will record it as a decimal. By definition, the AVcc cannot be less than the VA.

Management as AE: A decrease of more than 2 lines on the Snellen chart should be reported and managed as EA.

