#### **7.3.3.4 Corneal and conjunctival staining with fluorescein**

A drop of topical anesthetic will be instilled in the conjunctival fornix, then a drop will be applied. second drop on the tip of the fluorescein strip allowing it to sit on the strip for 5 seconds to elute the dye, shaking off the excess at the end. A small contact of the strip with the conjunctiva is made in the temporal fornix, while the patient looks up, without damaging the conjunctiva. It will be classified as according to the Oxford scale.[45]

The PI will record in the file and the eCRF the grade awarded for fluorescein staining of OD and OS respectively.

Management as AE: Corneal staining that is equal to or greater than grade III will be considered as AE.

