#### **7.3.3.6 Conjunctival hyperemia**

Conjunctival hyperemia is defined as the simplest reaction of the conjunctiva to a stimulus, it is seen a red appearance secondary to vasodilation of the conjunctival vessels of varying intensity. It will be graded using the Efron scale. [46] See appendix.

Management as AE: Conjunctival hyperemias classified as grade 3 or higher will be considered as AE. superiors.

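### The SAP plans to cross AEs with signs that the protocol itself counts as AEs: the overlap is complete for chemosis and depends on the cut-point for the other signs

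*SAP*

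**What the plan says.** The triangulation table in SAP 7.0 (the second of two tables numbered 3) sets out which variables are analysed against which. The AE row is "C1 | EAs | | | | TB | B | B | TB | TB | TB". Read against the column heads, AEs are crossed with acuity (D1) by B, and with stains (D2), hyperemia (D3) and chemosis (D4) by TB. The legend is "D. Descriptive statistics; T, 2x2 contingency table; B, Bivariate analysis; M, Multivariate analysis". The rows for the signs repeat the crossing in the AE column: "D2 | Ocular surface stains (TF and TVL). | DT | | | T | | | T", "D3 | Conjunctival hyperemia | TD | | DT | T | | | | T" and "D4 | Chemosis | TD | | DT | T | | | | | T". The acuity row carries a B there.

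The text of SAP 7.0 says that 2x2 tables are built to look for significant differences in qualitative variables, by Pearson chi-square or, where expected values are under 5, Fisher's exact test, at alpha 0.05.

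The protocol gives each sign its own AE rule:
- acuity (7.3.3.3): "A decrease of more than 2 lines on the Snellen chart should be reported and managed as EA"
- staining, with fluorescein (7.3.3.4) and in the same terms with lissamine green (7.3.3.5): "Corneal staining that is equal to or greater than grade III will be considered as AE"
- hyperemia (7.3.3.6): "Conjunctival hyperemias classified as grade 3 or higher will be considered as AE"
- chemosis (7.3.3.7): presence alone is an AE.

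The comfort index is treated differently: Protocol 7.3.3.2 says that its score alone is not an AE. Neither document removes sign-defined AEs from the AE variable in these tables, gives cut-points for them, or mentions the overlap.

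**The concern.** A test of association asks whether subjects with a sign have AEs more often than subjects without it. If the sign is itself recorded as an AE, every subject with the sign is an AE case by rule. The cell for sign present and no AE can then only be zero, and the null hypothesis of independence is false by construction. A small p-value would reflect the recording rule and say nothing about the product. With 22 subjects, very few cases are enough to produce one, and it could be reported as a relation between ocular signs and adverse events.

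**Working it through.** **How far each pair overlaps**, if C1 counts every AE:

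| Sign | Code, AE row / mirror | AE rule | Overlap |
|---|---|---|---|
| Chemosis | TB / T | any presence | complete |
| Hyperemia | TB / T | Efron grade 3 or more | complete if cut at grade 3, otherwise partial |
| Staining | TB / T | corneal grade III or more | complete for corneal staining cut at III; partial for other cuts or conjunctival staining |
| Acuity | B / B | loss of more than 2 lines | partial; no 2x2 table is planned |

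**Inputs.** n = 22 (SAP 5.0) and alpha 0.05 (SAP 7.0). Sidedness is not stated; two-sided is assumed. The plan gives no figure for these tables. Its sample size only supplies n: 18 x 1.2 = 21.6, rounded up to 22. With one to three sign subjects, no expected count in the sign row can exceed 3, so the SAP's own rule leads to Fisher's test.

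**Formula.** Let m subjects have the sign, all AE cases by rule, and let b other subjects have an AE. The table is [m, 0; b, 22 - m - b]. For the cases shown, the opposite tail adds nothing, so p = C(m+b, m) / C(22, m).

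- m = 1: p = (1+b)/22. With b = 0, 1/22 = 0.045. With b = 1, 2/22 = 0.09.
- m = 2: the denominator is 231. With b = 0, 1, 2, 3, 4, p = 1/231 = 0.004, 3/231 = 0.013, 6/231 = 0.026, 10/231 = 0.043, 15/231 = 0.065.
- m = 3: the denominator is 1540. With b = 0, 1/1540 = 0.0006. With b = 5, 56/1540 = 0.036. With b = 6, 84/1540 = 0.055.

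**At the AE rate the plan cites.** SAP 5.1 gives 30% for the 1.5% strength: 0.30 x 22 = 6.6, about seven AE subjects. If one of the seven has the sign, p = 7/22 = 0.32. If two do, p = 21/231 = 0.09. If three do, p = 35/1540 = 0.023.

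**Other denominators.** With 18 evaluable subjects, one sign subject and no other AE gives 1/18 = 0.056, and two sign subjects stay significant with up to two other AE subjects (6/153 = 0.039). The documents do not settle whether eyes are the unit here. If 44 eyes were used, one subject with a bilateral sign and no other AE would give 1/946 = 0.001.

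**How often it would happen.** The documents give no rates for these signs, so the rates here are assumptions. Let m be binomial(22, sign rate) and b binomial(22 - m, other-AE rate), and sum the probabilities of all tables with p at or below 0.05. The comparison lets AEs occur independently of the sign.

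| Sign rate | Other-AE rate | P(p <= 0.05), overlap | P(p <= 0.05), independent |
|---|---|---|---|
| 5% | 5% / 10% / 30% | 0.43 / 0.32 / 0.07 | 0.007 / 0.007 / 0.004 |
| 10% | 5% / 10% / 30% | 0.74 / 0.65 / 0.26 | 0.007 / 0.010 / 0.009 |
| 20% | 5% / 10% / 30% | 0.96 / 0.94 / 0.67 | 0.006 / 0.011 / 0.016 |

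The chance that no subject shows the sign is 0.95^22 = 0.32, 0.90^22 = 0.10 and 0.80^22 = 0.01 respectively. In that case nothing is forced.

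**The case against.** A reader might infer that the association is built in for all four signs, so that any p-value from these cells is empty. The documents do not support that.

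- **Cut-points.** The zero cell needs the sign to be split at its AE grade. The SAP keeps hyperemia on 0 to 4 and staining on 0 to 5 per panel, and names the outcomes as changes, while the AE rules use absolute grades. A subject who moves from grade 0 to grade 1 has a changed sign and no rule-based AE.
- **Staining and acuity.** The staining rule covers the cornea only, while the outcome includes the conjunctiva. Acuity is planned as a bivariate analysis of a Snellen value, by a method that is not named.
- **What C1 counts.** The row label is simply AEs, and the SAP's operational definition counts subjects with an AE over subjects exposed. Yet C1 sits beside the comfort index, where the primary outcome would be expected. If it counts only unexpected related AEs, a threshold sign also has to be judged unexpected and related, and no cell is fixed by rule.
- **Whether a test is meant.** The legend names tables and bivariate analyses. The test comes from the text of SAP 7.0, under an intra-group label. Some diagonal cells also carry T, and the mirror cells for stains, hyperemia and chemosis drop the B.
- **Size.** The 0.045 needs no other AE subject at all.

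These points limit the reach of the concern and all of them stand. They do not remove it. Chemosis is scored only as present or absent and any presence is an AE, so for all-AE counting no choice of cut-point is involved. The chemosis rule carries strike-through marks in the available text, but the same marks cover live procedure names in Protocol 7.4.1.1, so they are probably an artefact. If the rule had really been deleted, the point would still hold for hyperemia and corneal staining cut at the AE grade, and in part for acuity. Unstated cut-points, and an unstated meaning for C1, are themselves reasons to edit the table.

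**Conclusion.** The point holds in a limited form and is minor. Followed as written, the plan can produce a significant p-value that comes from the AE definition. The overlap is complete for chemosis, and for hyperemia or corneal staining cut at the AE grade, provided that C1 counts all AEs. Otherwise it is partial. At n = 22, two sign subjects are significant with up to three other AE subjects; one sign subject is significant only if nobody else has an AE. At about seven AE subjects it takes three with the sign. Over the assumed rates the chance of a definitional rejection runs from 0.07 to 0.96, against at most 0.016 under independence. If no healthy subject reaches a threshold, which is plausible, the result is an uninformative table and no false finding.

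A reader might also infer that the safety conclusion is compromised. It is not: Protocol 10.1.5 rests it on unexpected related AEs in under 10% of the study population, and these cells do not enter that rule. What is at risk is the interpretation of the supporting analyses.

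**What to change.** In the SAP triangulation table, delete the cells that cross C1 with D1 to D4 and their mirrors in the AE column. If the sponsor wants to keep them, compute each one with the AEs defined by that same sign taken out of C1, and state three things: the cut-point for the sign, whether C1 counts all AEs or only unexpected related ones, and whether the unit is the subject or the eye. In either case, add a listing of AEs that flags those that arose from a threshold sign. The cost is a table edit and one listing, with no new data. Deleting the cells also reduces the analysis work.
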